### **3.2.3.2. Nonclinical Studies**

A comprehensive series of nonclinical studies were conducted to support the clinical development of ALKS 8700 and are described in more detail in the ALKS 8700 Investigator's Brochure.

Results from genetic toxicity assays showed that ALKS 8700 was non-mutagenic in bacteria *in vitro* and was associated with chromosomal aberrations *in vitro* in human peripheral blood lymphocytes but not *in vivo* in rats. ALKS 8700 had limited capacity to inhibit human ether-à-go-go-related gene (hERG) potassium channel activity in a human cell line (i.e., concentration resulting in 50% inhibition of response [ $IC_{50}$ ] > 300  $\mu$ M). Inhibition of hERG current has been associated with increased duration of the cardiac action potential and prolongation of the QT interval.

General toxicology findings were generally similar to those described for DMF and consisted of target organ effects in kidney (tubular degeneration/necrosis with regeneration, tubular hypertrophy, and interstitial fibrosis in rats, mice, and/or monkeys), GI tract (mucosal hyperplasia of the nonglandular stomach and duodenum of rats and/or mice), bone (physeal dysplasia of proximal and distal femur and proximal tibia in monkeys), heart (inflammation/necrosis in rats), and testes (minimal degeneration in mice).

ALKS 8700 was evaluated for developmental and reproductive toxicity in rats and rabbits. In fertility studies in male and female rats, no notable fertility or embryonic developmental findings occurred. In embryo-fetal development studies in rats and rabbits, noteworthy findings of fetal vertebral malformations were observed in rabbits but not in rats.

The safety evaluation of ALKS 8700 and its metabolites (i.e., MMF, RDC-6567, and RDC-8439) was adequate as systemic exposures of these analytes in nonclinical studies were similar to or exceeded those in humans at the Phase 3 clinical dose of 924 mg/day (462 mg BID) of ALKS 8700. For the major human metabolites, MMF and RDC-6567, the exposures associated with adverse findings in nonclinical safety studies are detailed in the ALKS 8700 Investigator's Brochure.

Data generated through additional nonclinical studies will continue to be evaluated as they become available, including any potential influence on the risk-benefit profile of ALKS 8700.

CONFIDENTIAL

The information contained herein may not be used, disclosed, or published without the written consent of Biogen MA Inc.

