**Table 3: Clinical Laboratory Assessments**

Hematology 	Biochemistry	Urinalysis
Hematocrit	Sodium	Color
Hemoglobin	Potassium	pH
Red blood cell count	Chloride	Specific gravity
Total and differential (absolute) white blood cell count	Bicarbonate	Ketones
Platelets	Glucose	Protein
	Thyroid-stimulating hormone (TSH) 	Glucose
	Calcium	Bilirubin
	Uric Acid	Nitrite
	Creatinine	Urobilinogen
	Total protein	Occult blood
	Blood urea nitrogen	Microscopic examination of sediment only if urinalysis dipstick results are abnormal
	Albumin	Urine albumin
	Total bilirubin	Urine beta-2-microglobulin
	Alanine aminotransferase (ALT)	Urine creatinine
	Aspartate aminotransferase (AST)	
	Lactic dehydrogenase (LDH)	
	Alkaline phosphatase	
	Creatine phosphokinase	
	Lipid profile: blood cholesterol, high-density lipoprotein, low density lipoprotein, and triglycerides	

 Additional hematology assessments will be collected for subjects requiring follow-up for lymphopenia at the time of study completion or early termination.

 To be assessed at screening only.

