## **12.6. Methods of Analysis for Safety Endpoints**

The safety analysis will be carried out using the safety population. Reported AE terms will be coded using the Medical Dictionary for Regulatory Activities.

Safety assessments will be summarized using descriptive statistics along with supportive listings. The number and percentage of TEAEs will be summarized by system organ class, and preferred terms within each system organ class. SAEs and AEs resulting in treatment discontinuation will be summarized.

Observed values and change from baseline in laboratory parameters, vital signs, ECG parameters, and scores on the C-SSRS will be summarized by study visit. The number and percentage of subjects who have met potentially clinically significant criteria at any postbaseline visit will be summarized.

Listings will be provided for all safety endpoints.

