Biochemistry, Urinalysis, & Hematology Samples ⁹	X	X ⁵	X	X	X	X	X	X	X	X	X	X	X	X	X	X	X	
Vital Signs ¹⁰	X	X ⁵	X	X	X	X	X	X	X	X	X	X	X	X	X	X	X	
Standard 12-Lead ECG	X	X ⁵	X	X	X	X			X	X	X		X		X		X	
Pharmacokinetic Sampling ¹¹		X ⁵	X	X	X													
Timed 25-Foot Walk	X	X ⁵				X			X	X	X	X	X	X	X	X		

Visit	Screening	96-Week Open-Label Treatment ¹														
	1 ²	2 ³	3	4	5	6	7	8	9	10	11	12	13	14	15 /ET	16 Follow-up
Day	-21 to -1	1	15 (±3)	29 (±3)	57 (±5)	85 (±5)	113 (±5)	141 (±5)	169 (±5)	253 (±5)	337 (±5)	421 (±5)	505 (±5)	589 (±5)	673 (±5)	687 (±5)
Week	-3 to -1	1	2	4	8	12	16	20	24	36	48	60	72	84	96	98
EDSS	X	X ⁵				X			X	X	X	X	X	X	X	
SF-12		X ⁵							X		X		X		X	
EQ-5D-5L		X ⁵							X		X		X		X	
C-SSRS ¹²	X	X ^{3,4,5}	X	X	X	X	X	X	X	X	X	X	X	X	X	X
Concomitant Medication Review	X	X	X	X	X	X	X	X	X	X	X	X	X	X	X	X
Adverse Event Monitoring	X	X	X	X	X	X	X	X	X	X	X	X	X	X	X	X
Study Drug Dispensation		X	X	X	X	X	X	X	X	X	X	X	X	X		
Study Drug Accountability			X	X	X	X	X	X	X	X	X	X	X	X	X	
Emergency Treatment Card ¹⁵		X	X	X	X	X	X	X	X	X	X	X	X	X	X	

C-SSRS=Columbia Suicide Severity Rating Scale; ECG=electrocardiogram; EDSS=Expanded Disability Status Scale; EQ-5D-5L=EuroQol Group health outcome measure 5-level version; ET=early termination; [REDACTED]; SF-12=12-item Short Form health survey

Note: Two safety and tolerability assessments by phone will be conducted (one between Visits 2 and 3 and one between Visits 3 and 4)

¹ Unscheduled visit may occur at any time as per protocol requirements

² Only De Novo Subjects will participate in the screening visit

³ For Rollover Subjects, identical assessments taken at the last treatment visit in the antecedent study do not need to be repeated at Visit 2 in the current study

⁴ Eligible, consenting De Novo Subjects will give written consent at screening. Eligible, consenting Rollover Subjects will give written consent prior to participating in any study-specific procedures at Visit 2. Written confirmation of a subject's willingness to continue in the trial will be required if one or more of the following occur during the study: MS relapse, disability progression, [REDACTED]

⁵ To be conducted pre-dose at Visit 2

⁶ Full physical exam at screening. Brief physical exam, symptom-directed, at all other visits

⁷ For Rollover Subjects, height will be carried over from information recorded in the antecedent ALKS 8700 study in which they participated

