⁸ Serology testing includes hepatitis B surface antigen, hepatitis C antibody, and human immunodeficiency virus antibody

⁹ Urinalysis includes urine dipstick, urine microscopy (as applicable), urine beta-2-microglobulin, urine albumin, and urine creatinine

¹⁰Vital sign measurements include temperature, respiratory rate, blood pressure, and heart rate. Blood pressure, respiratory rate, and heart rate will be measured after the subject has been in a seated or supine position for at least 5 minutes

¹¹Pharmacokinetic samples will be collected in a subset of de novo subjects at selected sites. Samples will be collected pre-dose, and at 0.5, 1, 2, 3, 4, 6, and 8 hours after the morning dose on Days 1 and 29. Additional PK samples will be collected prior to and approximately 2-3 hours following the morning or evening dose on Days 15 and 57. Specifics of study visits where PK samples will be collected and PK sampling procedures will be provided to the study sites outside of this protocol.

¹⁴Use "Screening" version at screening; use "Since Last Visit" version at all other scheduled timepoints

¹⁵At Visit 2, dispense Emergency Treatment Card to De Novo Subjects and confirm possession/redispense if necessary for Rollover Subjects. At all other visits, confirm subject's possession of card and redispense if necessary

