3.6.5. Clinical Laboratory Parameters

Laboratory parameters will be presented in conventional units. Only scheduled laboratory parameters will be included in the summaries. All laboratory data, including those collected at unscheduled visits, will be included in the listings. Laboratory results (baseline and change from baseline) for chemistry and hematology parameters for each visit during the entire study will be summarized. Percent change of lymphocyte count for each visit will be summarized.

For urinalysis, the number and percentage of subjects with abnormalities at any post-baseline visit will be summarized. In addition, the number and percentage of subjects with values considered potentially clinically significant (PCS) occurring at any post-baseline visit for selected parameters will be summarized.

Clinical laboratory test values, scheduled or unscheduled, will be considered PCS if they meet PCS criteria listed in [Table 2](#). The percentages will be calculated relative to the number of

subjects with available non-PCS baseline values with respect to the specific criterion and at least 1 post-baseline assessment. The numerator is the total number of subjects with a non-PCS baseline value with respect to the specific criterion and at least 1 post-baseline PCS value. A supportive listing will present all values for a parameter for subjects with at least one PCS value for that parameter.

Shift tables for shift from baseline to any post baseline visits during treatment period will be provided for selected chemistry, hematology, and urinalysis parameters with conventional reference limits (limits provided by the performing laboratories) for the Safety Population.

The following graphical displays will be presented by enrollment group and overall:

- Mean along with the corresponding standard error (SE) for selected chemistry and hematology laboratory parameters.
- Boxplots will be used to display summary statistics for the last assessment, maximum and minimum change from baseline values for selected chemistry and hematology laboratory parameters.

Pregnancy and drug test data will be listed.

Table 2: Criteria for Potentially Clinically Significant (PCS) Laboratory Parameters

Category	Parameter	Criteria
Hematology	Hematocrit	$\leq 32\%$ and 3 point decrease from baseline (Female) $\leq 37\%$ and 3 point decrease from baseline (Male)
	Hemoglobin	≤ 9.5 g/dL (Female) ≤ 11.5 g/dL (Male)
	Neutrophils	$< 1.5 \times 10^3/\mu\text{L}$

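### SAP 3.6.5 leaves out, without declaring it, the by-visit summaries of quantitative urine markers that protocol 12.6 promises, so a gradual renal drift could be missed

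*SAP*

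**What the plan says.** Protocol 12.6 sets the rule for laboratory data: "Observed values and change from baseline in laboratory parameters, vital signs, ECG parameters, and scores on the C-SSRS will be summarized by study visit". It excepts no panel.

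SAP 3.6.5 divides the laboratory data. For two panels it plans by-visit results: "Laboratory results (baseline and change from baseline) for chemistry and hematology parameters for each visit during the entire study will be summarized". For the third it plans a count: "For urinalysis, the number and percentage of subjects with abnormalities at any post-baseline visit will be summarized". The planned mean plots and boxplots are also confined to chemistry and hematology.

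The quantitative urine tests belong to the third panel. Protocol Table 3 lists urine albumin, urine beta-2-microglobulin and urine creatinine in its urinalysis column. Footnote 9 to SAP Table 1 agrees: "Urinalysis includes urine dipstick, urine microscopy (as applicable), urine beta-2-microglobulin, urine albumin, and urine creatinine".

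Three other provisions of the SAP bear on these markers:
- Section 3.6.5 plans shift tables for selected urinalysis parameters, without saying which.
- The urinalysis criteria in SAP Table 2 cover dipstick glucose and dipstick protein only.
- Section 5, on changes from the protocol, mentions only COVID-19.

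On the kidney, protocol 3.2.3.2 reports "target organ effects in kidney (tubular degeneration/necrosis with regeneration, tubular hypertrophy, and interstitial fibrosis" among the nonclinical findings.

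**The concern.** The first objective is long-term safety over 96 weeks. For a continuous marker measured repeatedly, the natural questions are how far it moves, when, and whether it returns after the last dose. An any-visit abnormality count answers none of these. It records whether a limit was ever crossed and pools early, late and post-treatment visits.

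The protocol gives these markers a working role. Beta-2-microglobulin and the albumin-to-creatinine ratio are exclusion limits in protocol 6.2.2, and the ratio is also a threshold for withholding treatment in protocol 7.2. If the SAP is followed as written, the study report could contain no summary of how these markers changed over time, and nothing would tell a reader that the protocol had promised one.

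**Working it through.** **1. The two documents side by side**

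| Item | Protocol | SAP |
|---|---|---|
| By-visit observed value and change, chemistry and hematology | Yes (12.6) | Baseline and change by visit (3.6.5) |
| By-visit observed value and change, urinalysis | Yes, by the unrestricted wording of 12.6 | Not planned |
| Panel of the three quantitative urine tests | Urinalysis (Table 3) | Urinalysis (Table 1, footnote 9) |
| Albumin-to-creatinine ratio | Used in 6.2.2 and 7.2 | Not mentioned |
| Declared as a change | Not applicable | No (Section 5) |

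**2. What is collected.** Protocol Table 1 schedules urinalysis at the same visits as biochemistry and hematology. That is 13 on-treatment post-baseline visits (Visits 3 to 15) plus Visit 16, so 14 in all.

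**3. What the retained summaries can show.** The abnormality count pools all post-baseline visits, so it carries no timing and cannot separate Visit 16 from the rest. The shift tables cover the treatment period only, so they cannot show recovery. Both register only values that cross a laboratory limit.

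**4. Illustration of sensitivity.** The documents give no figure to reproduce. The following assumptions are not in the documents: a standardized marker on a scale where it is roughly normal, an upper limit at the 97.5th percentile, within-subject correlation ρ of 0.3 to 0.7, linear drift to Week 96, and 500 to 1000 subjects with Week 96 data.

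*Background with no drift.* If visits were independent with per-visit abnormal rate p, the share ever abnormal over 13 visits is 1 − (1 − p)^13:
- p = 1%: 12.2%
- p = 2.5%: 28.0%
- p = 5%: 48.7%

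Correlation lowers this. Simulated values for subjects normal at baseline are in the table below.

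*By-visit alternative.* The Week 96 mean change divided by its standard error is d / (√(2(1 − ρ)) / √n), where d is the drift in SD units. With d = 0.3, ρ = 0.5 and n = 500, this is 0.3 × 22.36 / 1 = 6.7.

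| ρ | Ever abnormal, no drift | Ever abnormal, drift 0.3 SD | Week 96 mean change in standard errors, n = 500 to 1000 |
|---|---|---|---|
| 0.3 | 20.4% | 25.7% | 5.7 to 8.0 |
| 0.5 | 15.3% | 19.5% | 6.7 to 9.5 |
| 0.7 | 10.2% | 13.4% | 8.7 to 12.2 |

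The drift adds 3.2 to 5.3 percentage points to a background that is itself unknown. The 19.5% with drift at ρ = 0.5 is below the 20.4% without drift at ρ = 0.3. In a single-arm study, the any-visit percentage alone could not tell these two situations apart. By-visit change uses each subject's baseline as the reference and does not depend on that background.

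**The case against.** The strongest reply is that the renal safety picture is not empty, and this stands. The SAP keeps the any-visit abnormality count, shift tables for some urinalysis parameters, a criterion for dipstick protein, full laboratory listings, and Renal Injury as an adverse event category of special interest. Serum creatinine and blood urea nitrogen, both chemistry tests, are summarized by visit. A reader might infer that a renal signal would go unseen, or that each subject's serial data shrink to one yes/no value. The documents support neither: a large shift past a limit could appear in several places, and no data are lost.

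These provisions still do not fill the gap. Listings are not a summary. Under protocol 11.1.1 an abnormal result becomes an adverse event only if it is serious, needs corrective therapy or is judged clinically significant. Serum creatinine and urea do not measure urinary albumin or beta-2-microglobulin.

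A second reply is that protocol 12.1 leaves details to the SAP, that SAP Section 7 promises general summary statistics, and that mock tables and dataset specifications are separate documents not available here. Those might add the missing tables or name the selected parameters. But Section 7 names no urine parameter and gives no visit rule of its own for them, and 3.6.5 treats urinalysis separately. Removing a whole panel from a stated summary is a change, not a detail.

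A reader might also infer that the markers are collected because kidney is a target organ. The documents do not give that reason. Protocol 3.2.3.2 lists kidney with GI tract, bone, heart and testes, and calls the findings generally similar to those for DMF.

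Finally, there is no control arm and no hypothesis, so a by-visit drift could be described but not attributed to the drug. That is right, and it applies equally to every laboratory summary in the plan.

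**Conclusion.** The point holds in a limited form. SAP 3.6.5 narrows protocol 12.6 without declaring it, and the narrowing removes every planned summary of the size, timing and post-treatment recovery of change in urine albumin, beta-2-microglobulin and creatinine. A gradual or sub-threshold drift could be missed; a large shift past a reference limit probably would not be. This conclusion rests on the text alone.

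The illustration indicates scale only. Across correlations of 0.3 to 0.7 and 500 to 1000 subjects, a 0.3 SD drift lies 5.7 to 12.2 standard errors from zero in the by-visit mean change, yet moves the any-visit percentage by about 3 to 5 points. Actual variability, skewness, retention and enrollment-group sizes are not in the documents. It would therefore be wrong to read into this a specific small percentage shift that the study could detect, and nothing here shows that a drift of any given size matters clinically.

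This should be corrected, but it does not threaten the study: the analysis is descriptive, the data exist and the tables can be added.

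**What to change.** In SAP 3.6.5, extend the by-visit summary of observed value and change from baseline, through Visit 16, to urine albumin, urine beta-2-microglobulin, urine creatinine and the albumin-to-creatinine ratio. Because these markers are likely to be skewed, use median and quartiles, or the geometric mean ratio to baseline. Put any figure on the same scale, not arithmetic mean with standard error.

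Name the urinalysis parameters selected for shift tables.

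The three measured markers restore what protocol 12.6 states. The ratio is an addition, since protocol Table 3 does not list it as a parameter, and its use in protocol 6.2.2 and 7.2 justifies it. If the sponsor prefers to keep the narrower summary, SAP Section 5 should at least declare and justify it, though that would leave the gap in place.

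The cost is SAP wording and one or two tables from data already collected. No assessment, threshold or treatment rule changes.

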  - Estimated glomerular filtration rate (eGFR)  $\leq$  60 mL/min/1.73 m^2 (using the Chronic Kidney Disease Epidemiology Collaboration equation) [\[Levey 2009\]](#)
  - Lymphocyte count  $< 0.9 \times 10^3/\mu\text{L}$
11. Has any of the following abnormal urine tests at screening:
  - Beta-2 microglobulin  $> 0.3 \mu\text{g/mL}$
  - Albumin to creatinine ratio  $> 200 \text{ mg/g}$
12. Has a clinically significant history of suicidal ideation or suicidal behavior occurring in the past 12 months as assessed by the C-SSRS at screening.
13. Has previously discontinued treatment with Tecfidera due to tolerability issues and/or lack of efficacy.
14. Has a history of treatment with or has received the following:
  - Total lymphoid irradiation, cladribine, T-cell or T-cell receptor vaccination, total body irradiation, or total lymphoid irradiation at any time
  - Stem cell transplantation at any time
  - Mitoxantrone or other immunosuppressant agents (e.g., cyclosporine, cyclophosphamide, methotrexate, mycophenolate) within 2 years prior to Visit 2

CONFIDENTIAL

The information contained herein may not be used, disclosed, or published without the written consent of Biogen MA Inc.

- Teriflunomide within 2 years of Visit 2, unless the serum/plasma concentration of teriflunomide is < 0.020 µg/mL (< 20 ng/mL) prior to Visit 2 (an accelerated elimination procedure for teriflunomide with cholestyramine is permitted during screening)
- Natalizumab within 2 months prior to Visit 2 or any prior use of alemtuzumab
- Fingolimod within 90 days prior to Visit 2
- Daclizumab within 6 months prior to Visit 2
- B-cell targeted therapies for the treatment of MS (e.g., ocrelizumab, rituximab) within 12 months of screening; greater than 12 months of screening is permissible with evidence that the CD19 cells have returned to within normal range (per local laboratory reference range)
- Eligibility related to prior treatment with an investigational drug and/or a commercially available drug for the treatment of MS not listed above within the past 24 months will be determined on a case-by-case basis by the Medical Monitor
- Steroids, with the exception of topical or inhaled steroids, or intravenous (IV) immunoglobulin within 30 days prior to Visit 2

15. Current or prior participation in a clinical trial within 3 months of screening.

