### 7.2. Modification of Dose and/or Treatment Schedule

Starting on Day 8 of treatment, dose reduction to ALKS 8700 231 mg BID is permitted at the Investigator's discretion for subjects who are unable to tolerate ALKS 8700 462 mg BID. Once a subject has stabilized after dose reduction, attempts should again be made to achieve and maintain the target maintenance dose of ALKS 8700 462 mg BID. If a subject remains unable to tolerate ALKS 8700 462 mg BID after 1 month on treatment (i.e., by Visit 4), further dose reduction will not be permitted, and the subject will be discontinued from the study.

In the event of a suspected relapse (new symptoms or worsening symptoms), subjects will be asked to call the treating neurologist within 48 to 72 hours of the onset of the symptoms to determine the necessity of an Unscheduled Relapse Visit. An Unscheduled Relapse Visit will be conducted as described in Section 5.4. Further instruction is also provided in Section 7.2.2.

Should progressive multifocal leukoencephalopathy (PML) be suspected by the treating neurologist based on symptoms or signs during the relapse visit, study treatment will be withheld and an appropriate diagnostic work-up should be performed as soon as possible (within 14 days of the relapse visit). If PML is excluded based on the diagnostic work-up, the subject may resume taking study treatment if approved by the Medical Monitor. If the diagnostic work-up exceeds 14 days, the subject will be discontinued from the study. Should a diagnosis of PML be confirmed, the subject will be discontinued from the study and provided with appropriate medical care.

If serious infection occurs, study treatment should be withheld until it has resolved.

CONFIDENTIAL

The information contained herein may not be used, disclosed, or published without the written consent of Biogen MA Inc.

Study treatment must also be temporarily withheld if any of the following laboratory parameters meet the following threshold limits:

- AST or ALT  $> 3 \times \text{ULN}$ ; confirmed by repeat testing as soon as possible. If the value remains  $> 3 \times \text{ULN}$  for  $\geq 4$  weeks after discontinuation of study treatment, the subject must permanently discontinue study treatment.

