- Lymphocyte count  $< 0.5 \times 10^9/\text{L}$ ; confirmed by repeat testing as soon as possible. If the value remains  $< 0.5 \times 10^9/\text{L}$  for  $\geq 4$  weeks after discontinuation of study treatment, the subject must permanently discontinue study treatment. (Subjects who permanently discontinue the study with a last measured lymphocyte count  $< 0.8 \times 10^3/\mu\text{L}$  will require additional follow-up to monitor their lymphocyte counts.)
- eGFR  $< 60 \text{ mL/min}/1.73 \text{ m}^2$ ; confirmed by repeat testing as soon as possible. If the eGFR remains  $< 60 \text{ mL/min}/1.73 \text{ m}^2$  for  $\geq 4$  weeks after discontinuation of study treatment, the subject must permanently discontinue study treatment.
- Urine albumin to urine creatinine ratio  $> 200 \text{ mg/g}$ ; confirmed by repeat testing as soon as possible. If the urine albumin to urine creatinine ratio remains  $> 200 \text{ mg/g}$  for  $\geq 4$  weeks after discontinuation of study treatment, the subject must permanently discontinue study treatment.

Resuming study treatment after it has been withheld is to be considered on a case by case basis and must be discussed with the Medical Monitor.

The study may be stopped at any time or study sites may be closed at the Sponsor's discretion.

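### The SAP's PCS laboratory table has rows for the protocol's liver and lymphocyte withholding limits but none for its two renal limits, so crossing eGFR <60 or urine albumin/creatinine >200 mg/g is not itself counted

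*SAP*

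**What the plan says.** Protocol section 12.6 commits to a PCS summary: "The number and percentage of subjects who have met potentially clinically significant criteria at any postbaseline visit will be summarized". It names no parameters or cut-offs. SAP section 3.6.5 supplies them: "Clinical laboratory test values, scheduled or unscheduled, will be considered PCS if they meet PCS criteria listed in" Table 2. The percentages there use subjects who were not PCS at baseline on the criterion in question and who have at least one post-baseline value.

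Protocol section 7.2 separately lists laboratory limits that interrupt dosing: "Study treatment must also be temporarily withheld if any of the following laboratory parameters meet the following threshold limits". There are four: AST or ALT >3 × ULN, lymphocytes <0.5 × 10⁹/L, eGFR <60 mL/min/1.73 m², and urine albumin/creatinine ratio >200 mg/g. Each requires confirmation by repeat testing. Permanent discontinuation follows only if the value stays beyond the limit for at least 4 weeks off treatment.

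The kidney-related rows of SAP Table 2 are serum creatinine ≥2 mg/dL, BUN >30 mg/dL and dipstick protein of at least 2+. Protocol Table 3 includes serum creatinine, urine albumin and urine creatinine in the laboratory panel, so both renal quantities can be derived.

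**The concern.** Long-term safety is the first objective of the study. Protocol section 3.2.3.2 lists the kidney among the organs affected in toxicology studies, and SAP section 3.6.4 makes renal injury an adverse event category of special interest. The protocol considered two renal laboratory limits important enough to interrupt dosing. A reader of the study report would expect to find how many subjects crossed them, as can be found for transaminases and lymphocytes. Under the SAP as written, a subject could cross a renal limit and not appear as PCS for that reason. The renal part of the PCS table would then rest on creatinine, BUN and dipstick criteria that the documents do not relate to those limits.

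**Working it through.** **Step 1. Match each withholding limit (protocol section 7.2) to a row of SAP Table 2.**

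| Protocol limit | Table 2 row on the same parameter | Match |
|---|---|---|
| AST or ALT >3 × ULN | ALT ≥3 × ULN; AST ≥3 × ULN | Yes (differs only at exactly 3 × ULN) |
| Lymphocytes <0.5 × 10⁹/L | <0.5 × 10⁹/L | Yes, identical |
| eGFR <60 mL/min/1.73 m² | none | No |
| Urine albumin/creatinine >200 mg/g | none | No |

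Result: 2 of 4 overall and 0 of 2 renal. With two rows added, it would be 4 of 4 and 2 of 2.

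**Step 2. Look for another planned summary set at either renal limit.**

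- SAP 3.1.1.4 and 3.6.2: GFR is used only as a baseline subgroup variable.
- SAP 3.6.5, by-visit summaries: chemistry and hematology only. Protocol Table 3 classes urine albumin and urine creatinine as urinalysis and does not list eGFR.
- SAP 3.6.5, urinalysis abnormality count: no limit is stated.
- SAP 3.6.5, shift tables: unnamed selected parameters, against laboratory reference limits.
- SAP 3.6.5, listings: all values are shown, but a listing is not a count, and the supportive PCS listing is triggered only by a Table 2 value.
- SAP 3.6.4, renal injury: an adverse event category. Under protocol 11.1.1 an abnormal result is an adverse event only if it is serious, needs specific corrective therapy or is judged clinically significant by the investigator. Withholding treatment is not one of those criteria.
- SAP 3.4: exposure runs from first to last dose plus 1 day. No summary of temporary withholding is planned.

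None of these counts post-baseline eGFR <60 or a ratio >200 mg/g.

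**Step 3. Illustrate how far the creatinine row is from the eGFR limit.** Protocol section 6.2.2 names the CKD-EPI equation but does not print its coefficients. I assume the 2009 set. For creatinine above κ:

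eGFR = 141 × (Scr/κ)^−1.209 × 0.993^age × s,

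with κ = 0.7 and s = 1.018 for women, κ = 0.9 and s = 1 for men, and no race term.

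- Woman aged 40 at 2.0 mg/dL: 141 × (2.0/0.7)^−1.209 × 0.993^40 × 1.018 = 30.5.
- Man aged 40 at 2.0 mg/dL: 141 × (2.0/0.9)^−1.209 × 0.993^40 = 40.5.

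Solving the same equation for eGFR = 60 and running over ages 18 to 65:

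| | eGFR at creatinine 2.0 mg/dL | Creatinine at eGFR 60 |
|---|---|---|
| Women | 35.5 (age 18) to 25.6 (age 65) | 1.30 to 0.99 mg/dL |
| Men | 47.3 (age 18) to 34.0 (age 65) | 1.64 to 1.25 mg/dL |

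Multiplying by a race term of 1.159 gives 29.6 to 54.8 at creatinine 2.0 across both sexes, still below 60 throughout. On these assumptions there is a band of creatinine values that meets the eGFR limit without reaching the creatinine row.

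**Step 4. The ratio and the dipstick row.** At 200 mg/g, urine albumin is 0.2 × urine creatinine in the same units: 10, 20 and 40 mg/dL for assumed urine creatinine of 50, 100 and 200 mg/dL. The dipstick row is a grade with no adjustment for urine creatinine, and the documents give no concentration for 2+. The overlap between the two criteria cannot be sized.

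**The case against.** The strongest objection is that PCS limits need not mirror withholding limits. Protocol section 12.6 prescribes no parameters, SAP section 3.6.5 speaks of selected ones, and neither document ties PCS to section 7.2. That stands: this is a reporting gap, not a contradiction. It does not explain why the liver and lymphocyte limits have rows and the renal ones do not.

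It is also fair that renal data are not ignored. The creatinine, BUN and dipstick rows can catch some subjects, and the urinalysis counts, possible shift tables, renal injury events, discontinuation tables and listings all carry relevant information. The table shells and programming specifications are separate documents that might add to this. As specified in the SAP, though, none is set at the two limits.

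Three stronger readings are tempting and should be resisted.

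- A reader might infer that beta-2-microglobulin needs a PCS row too. It is collected, but its only limit, 0.3 µg/mL, belongs to the De Novo exclusion list ("Has any of the following abnormal urine tests at screening"). It is not a withholding limit, so a PCS row at that value would be a new on-treatment threshold without support in the documents.
- A reader might infer that the PCS table will show hardly any renal abnormality while subjects come off drug. The documents give no incidence to support that.
- A reader might equate a value beyond the limit with a withheld subject. The protocol requires each crossing to be "confirmed by repeat testing as soon as possible. If the eGFR remains" below 60 for at least 4 weeks, in the case of eGFR, before discontinuation becomes permanent. One value is neither a confirmed crossing nor a discontinuation.

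**Conclusion.** The point holds as a gap in planned reporting. SAP Table 2 covers two of the protocol's four withholding parameters and neither of the renal two, and no other summary described in the SAP counts crossings of eGFR 60 or of 200 mg/g. This rests on setting the two documents side by side and needs no outside figure. The eGFR range of about 26 to 47 at creatinine 2 mg/dL (about 30 to 55 with the race term) is an illustration under assumed coefficients. It suggests that the creatinine row would miss many crossings of the eGFR limit, but not how many subjects that would be.

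It does not follow that these subjects go wholly uncounted or that renal risk will be understated in the report. Nor should the three uric acid cut-offs in the same table (>9, >8 for women, >10 for men) be read as a contradiction. PCS percentages are computed criterion by criterion, so each cut-off can be reported separately. The weight is modest: an inexpensive improvement worth making in a study whose main purpose is safety.

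**What to change.** Add two rows to SAP Table 2, or an equivalent post-baseline count by enrollment group and overall: eGFR <60 mL/min/1.73 m² and urine albumin/creatinine ratio >200 mg/g. Both figures are already in protocol section 7.2, so no new clinical threshold is introduced. Derive eGFR from serum creatinine with the equation named in protocol section 6.2.2, stating the coefficients and whether a race term is used. Derive the ratio from urine albumin and urine creatinine. Keep the existing Table 2 denominator rule. Add a footnote saying that the rows count subjects with any qualifying value, not subjects whose treatment was withheld after a confirmed result.

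The cost is two derivations, two table rows and a footnote, with no new data collection and no change to subject management. The downside is a small amount of extra programming and a renal table that may look less favourable.
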